Power analysis was performed to estimate an adequate sample size to support statistical conclusion validity and so that correct inferences can be made about the relationships between study variables. The standardized effect size was calculated to equal 0.5. Assuming an alpha of 0.05, power of 0.80 and a standardized effect size of 0.5, 64 patients will be required for each treatment group based on anticipated difference in patient reported pain scores due to sciatic PNB technique. Projected sample sizes were increased approximately ten percent from 64 per group to total of 70 subjects per group in an effort to account for patient attrition and lost data, therefore, a total of 140 patients will be enrolled in the study. Additionally, if the loss in patients is unequal between groups, yielding a significant disparity between study group composition, additional subjects may be added to account for this unequal loss.

Despite the presence of multiple confounding variables, the calculated sample size is sufficient to determine if a significant difference in outcomes measures exists secondary to sciatic PNB technique. Additionally, the sample size does not need to be altered based on the equation: $N > 50 + 8k$, where N is the number of cases and k is the number of predictors (Warner, 2013). In this study there is only one predictor, sciatic PNB technique, which is anticipated to impact outcomes following ACL reconstruction.

E. Randomization:

A computer generated randomization scheme will be used to assign 70 patients to each treatment group. The randomization will be done using the maximum allowable percent deviation method. This algorithm conducts a search to find a randomization list for which all percent deviations are less than or equal to the maximum allowable percent deviation of 10%. The randomization scheme will be sent to the PI who will then prepare and maintain a log of subject assignments. The PI will notify the participating surgeon and anesthesia team of the treatment (single-injection or continuous sciatic PNB) that is to be given to the next consented patient. The research coordinator will remain blinded to the assigned treatment plan until data collection has been completed.

F. Components of Cincinnati Children's Hospital Medical Center to be Utilized for this Study:

Subjects undergoing unilateral ACL reconstruction with a hamstring autograft on an outpatient basis at the Liberty Campus of CCHMC will be recruited from the OR schedule.

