The hypothesis that the extended duration of analgesia offered by continuous sciatic PNB decreases the incidence of unplanned admission due to poor pain control during the initial 72 hours following hamstring autograft harvest when compared to single-injection sciatic PNB will be tested with the Chi-square test. The Chi-square test is used to determine if there is a relationship between two categorical variables (Field, 2009). As the data for this DV are categorical, the focus during analysis is placed on frequencies rather than means. The Chi-square test can be used to determine if there is a significant difference between the expected frequencies and observed frequencies in one or more categories (Field, 2009).

The hypothesis that the extended duration of analgesia offered by continuous sciatic PNB does not delay active knee flexion during the initial 72 hours following hamstring autograft harvest when compared to single-injection sciatic PNB will be tested using the Wilcoxon Mann Whitney test. The hypothesis that the extended duration of analgesia offered by continuous sciatic PNB improves patient satisfaction during the initial 72 hours following hamstring autograft harvest when compared to single-injection sciatic PNB will also be tested using the Wilcoxon Mann Whitney test. The Wilcoxon Mann Whitney test is appropriate to test both these hypotheses, as this test is designed to evaluate the difference between two treatments (single-injection sciatic PNB and continuous sciatic PNB) using data from an independent measures study (Gravetter & Wallnau, 2000). During analyses, testing may be altered based on the recommendations of the statistician to better analyze the collected data. Intention-to-treat analysis will not be employed, as this may skew results and it is often difficult to obtain outcome data for study participants who have dropped out of the study (Polit & Beck, 2012).

Prior to any analyses, the distribution of the demographic variables will be compared between the two treatment groups. All statistical tests will be two-sided with a significance level of $\alpha=0.05$ and will be conducted using SAS[®] software, (Version 9.2, Cary, NC). Following the enrollment of the initial 30 subjects (with 15 in each study group), an interim analysis utilizing the statistical tests later described will be performed to determine if statistically

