significant differences exist between the outcome measures of each sciatic PNB technique. Performing an interim analysis limits the number of patients exposed to study procedures. If statistically significant differences exist such that one of the two sciatic PNB techniques clearly produces superior patient outcomes, the study will be stopped. However, should the outcomes measures of each sciatic PNB technique be found to be equivalent and without statistically significant differences enrollment will continue.

VII. DATA SAFETY AND MONITORING

Adverse events will be collected until data collection is complete. Adverse events will be recorded on the case report forms. Details will include an explanation of the event, seriousness, anticipation, treatment, resolution and relatedness to the study treatment. All study-related adverse events will be followed through to completion

A. Adverse Event Definitions:

The definitions for adverse event, adverse device effect, serious adverse event, serious adverse device effect, and unanticipated adverse device effect are provided below (ANSI/AAMI/ISO 14155-2:2003, 21 CFR 812.3(s)).

Adverse Event: an adverse event is any untoward medical occurrence in a subject, which need not be related to the treatment under investigation.

Adverse Peripheral Nerve Blockade Blockade Effect: an adverse peripheral nerve blockade effect is any untoward or unintended response to regional blockade, which may result from insufficiencies in the deployment of the ultrasound machine, or from provider error.

Serious Adverse Event: a serious adverse event is an adverse event that results in death, inpatient hospitalization, severe or permanent disability, a life threatening illness or injury, fetal distress, fetal death, a congenital abnormality, a birth defect, or medical or surgical intervention to prevent permanent impairment to body or structure.

Serious Adverse Peripheral Nerve Blockade Effect: a serious adverse peripheral nerve blockade effect is an adverse regional blockade effect that results in death, inpatient hospitalization, and severe or permanent disability or is life threatening.

Unanticipated Peripheral Nerve Blockade Effect: any serious adverse effect on health or safety or any life threatening problem or death caused by, or associated with, peripheral nerve blockade if the effect, problem, or death was not previously identified in nature, severity or degree of incidence in the

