The Data Safety Monitoring Committee will meet to review the results of the study to date following the enrollment of the 30 participants, 60 participants, and 90 participants. In addition, the Data Safety Committee shall convene if 2 or more study-related adverse events occur related to this study. The Data Safety Monitoring Committee shall be comprised of 2 members of the Department of Anesthesia credentialed by CCHMC to perform peripheral nerve blockade but who are not part of this study ([name] and [name]), a statistician, and a patient advocate. The patient advocate will be the parent of a patient who has previously undergone ACL reconstruction at the Liberty Campus of CCHMC.

VIII. PRIVACY AND CONFIDENTIALITY

All subjects screened and enrolled in this study will be identified only by their initials and/or assigned study number only. Data confidentiality will be maintained by data being stored in a password protected computer and hard copies of subject information stored in a locked office. All information collected will be treated as confidential, as provided by law. The study records will be made available for review only to the Institutional Review Board (IRB) and the Food and Drug Administration (FDA). The subjects' names or any identifier will not be used in published information relating to this study.

IX. FUNDING

This is a CCHMC investigator initiated study that has received financial support from the AANA Foundation.

X. COST AND PAYMENT FOR PARTICIPATION

The patient's insurance company will be charged for all PNB and associated equipment utilized in this observational study. This is not a departure from standard practice of care, as PNB is routinely employed for postoperative pain control following ACL reconstruction with a hamstring autograft in the adolescent population.

Patients undergoing surgery with [name] will not receive any charges related to PNB as they will not receive PNB per his discretion.

The patient's insurance company may be charged for continuing medical care and/or hospitalization including tests and treatments of any side effects of the study treatment that may occur. In the event that the insurance does not cover all costs, patients may incur additional costs because of treatment side effects.

A \$20.00 gift card will be distributed as incentive to all participants who enroll in this study. The gift card will be mailed upon completion of the data collection process during the three days following surgery.

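### The interim look at 30 of 140 patients can stop the trial on unadjusted significance at 0.05 with no defined boundary, so type I error on pain alone is about 9%, not 5%

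*Combined protocol and SAP*

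**What the plan says.** Section VI.B (Primary Endpoint Analysis) gives one error rate for the whole plan: "All statistical tests will be two-sided with a significance level of" 0.05. The next sentence introduces the early look: "Following the enrollment of the initial 30 subjects (with 15 in each study group), an interim analysis utilizing the statistical tests later described" is to establish whether the outcome measures differ significantly between the two techniques. The stopping rule follows: "If statistically significant differences exist such that one of the two sciatic PNB techniques clearly produces superior patient outcomes, the study will be stopped". Enrollment continues if no significant difference is found.

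The interim sentence points to tests described later. The tests are in fact described earlier in the same section, and nothing after it supplies an interim threshold. No boundary, alpha spending or adjusted final level appears anywhere in the document.

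Section V.D bases the sample size on a single analysis, with pain scores as the outcome: "Assuming an alpha of 0.05, power of 0.80 and a standardized effect size of 0.5, 64 patients will be required for each treatment group". Separately, Section VII.D has the monitoring committee "review the results of the study to date following the enrollment of the 30 participants, 60 participants, and 90 participants".

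**The concern.** A trial that tests the same hypothesis twice at 0.05, and can claim a result either time, has more than a 5% chance of a false claim. Here the first test comes at about a fifth of the planned enrollment.

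A stop at that point ends randomization for good. The effect estimate would come from 15 patients per group and would be selected for being large. The outcomes on the other side of the trade-off set out in Section I, above all active knee flexion, would be left with very little data. The rule also does not say what happens when results are mixed, for example less pain but poorer knee flexion.

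**Working it through.** **Inputs.** Two-sided alpha 0.05 for all tests (VI.B). Standardized effect 0.5, power 0.80, 64 per group raised to 70, total 140 (V.D). Interim at 30 patients, 15 per group (VI.B).

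**The plan's own sample size.** The normal approximation gives n = 2(1.96 + 0.8416)²/0.5² = 62.8, so 63 per group. The t-test gives 63.77, so 64, with power 0.801. The stated 64 is reproduced, and 64 × 1.1 = 70.4 agrees with the stated 70. The figure is a standard single-look calculation with no allowance for an interim test.

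**Type I error with two looks at one outcome.** The outcome is the average pain score. Section VI.B tests it by Pearson's correlation. With a two-valued group variable, that gives the same p-value as a two-sample t-test.

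- Information fraction: t = 30/140 = 0.214. If only the 64 per group needed are evaluable, t = 30/128 = 0.234.
- Under the null, the interim and final statistics are approximately bivariate normal with correlation √t = 0.463 (or 0.484).
- Error = P(|Z₁| > 1.96 or |Z₂| > 1.96) = 0.05 + 0.05 − P(both exceed).
- For t = 0.214, P(both exceed) = 0.0083, so error = 0.0917. For t = 0.234, error = 0.0912.
- Simulated t-tests at 15 and then 70 or 64 per group give 0.091 to 0.092.

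**The early look if the planned effect of 0.5 SD is true.**

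- Power of the t-test with 15 per group: 0.262.
- Smallest significant difference: 2.048 × √(2/15) = 0.748 SD, taking the SD as known.
- Mean observed difference among trials significant at this look (simulation): 0.93 SD, which is 0.93/0.5 = 1.9 times the truth.

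**Boundaries that hold total two-sided error at about 0.05 for one named outcome (t = 0.214).**

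| Interim | Final | Total error |
|---|---|---|
| p < 0.05 | p < 0.05 | 0.092 |
| p < 0.001 | p < 0.05 | 0.0506 |
| p < 0.001 | p < 0.049 | 0.0496 |
| p < 0.0267 (Pocock) | p < 0.0267 | 0.050 |
| about p < 0.000003 (O'Brien-Fleming-type) | p < 0.0500 | 0.050 |

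With the p < 0.001 and 0.049 pair, power at 70 per group and 0.5 SD is 0.84, the same to two decimals as with no interim look. At the planned effect the interim threshold is crossed about 2% of the time.

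**The case against.** The best defense is that significance alone does not stop the trial. The stopping sentence also requires that one technique be clearly superior, and it speaks of outcomes in the plural. If all five outcomes had to be significant in the same direction, the error on pain would be only 0.050 to 0.053. This stands as a possible reading. The plan does not state it, and the continuation clause, which depends only on the absence of significant differences, points the other way. A rule that can give either 5% or 9% has to be written down.

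A reader might go further the other way and infer that significance on any one of the five outcomes stops the trial. Simulation under that reading, with assumed correlations of 0.3 to 0.5, gives false-positive rates of 31% to 36% over both looks. The documents do not support presenting that as the size of this problem, for three reasons:

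- The any-outcome rule is not in the text.
- The correlations are assumed, and the simulation treats unplanned admission, a yes/no outcome, as normally distributed.
- Five outcomes tested once at the end, with no interim, already give 18% to 21%. Most of the figure therefore comes from multiplicity, and the 0.05 is stated per test.

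A reader might also count the committee reviews at 60 and 90 patients as efficacy looks, which would give about 13% for one outcome. Section VII.C describes the committee's task in terms of adverse events and patients' best interest, and no efficacy test is attached to those reviews. Section VII.D does say that results will be reviewed, so a clarifying sentence is worth adding, but 13% is not what the plan delivers.

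**Conclusion.** The concern holds for the stopping rule as written. It is unadjusted, it has no boundary, and neither the governing outcome nor clear superiority is defined. The firm figure is a type I error of about 9% for pain alone against the stated 5%. It assumes that significance at 0.05 on average pain is enough to stop, and that the final test is also at 0.05. The true rate could be higher or lower, depending on a rule the plan has not given.

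The exaggeration of the effect after an early stop (about 0.93 SD for a true 0.5 SD) assumes approximately normal average scores and the plan's own effect size. The defect should be corrected before the interim data are examined, because the rule decides whether the trial ends at 30 of 140 patients.

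**What to change.** In Section VI.B, replace the stopping and continuation sentences with one of two options.

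1. The look at 30 patients is for safety only, with no comparison of efficacy outcomes. The final test stays at 0.05.
2. One pain outcome governs the interim. The plan must name it first, because Section VI.B now tests pain both as a 72-hour average and separately at each 12-hour period. The average score already planned is a natural choice. The trial may stop for efficacy only if that outcome reaches two-sided p < 0.001 at 30 patients. Otherwise it is tested at 0.049 at the end, for a total error of about 0.0496.

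In Section VII.D, state that the committee reviews at 30, 60 and 90 patients carry no other efficacy stop. The committee's safety powers in Section VII.C are unaffected.

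The cost is a few sentences and, for option 2, a prior decision on the governing pain outcome. No patients are added and almost no power is lost. The real price is that an early stop for benefit becomes rare, about 2% at the planned effect. This largely gives up the interim's stated aim of limiting how many patients are exposed to study procedures. Neither option deals with multiplicity across the five outcomes, which needs its own statement.

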Anterior cruciate ligament reconstruction utilizing a hamstring autograft is a surgical technique that has gained popularity among orthopedic surgeons caring for adolescent patients. While utilization of a hamstring autograft is a revered technique, harvest of the hamstring yields significant pain. Sciatic peripheral nerve blockade has proven to reliably provide analgesia at the hamstring donor site. Single-injection sciatic peripheral nerve blockade is considered a basic and effective technique, making its use following anterior cruciate ligament reconstruction standard practice in many institutions. The duration of action of single-injection sciatic peripheral nerve blockade may fail to outlast the pain arising from the hamstring donor site, prompting some clinicians to employ continuous sciatic peripheral nerve blockade via an indwelling catheter. A lack of comparative effectiveness studies exists in the literature regarding the duration of action of peripheral nerve blockade necessary to adequately provide pain control following hamstring autograft harvest, resulting in disagreement among clinicians as to best pain control practices. Proponents of continuous sciatic peripheral nerve blockade assert that while more costly, the extended duration of analgesia afforded by this technique improves pain control postoperatively and decreases the use of other pain medications. Advocates of single-injection sciatic peripheral nerve blockade cite concerns associated with continuous sciatic peripheral nerve blockade known to be detrimental to rehabilitation, such as decreased active knee flexion and increased risk of falls. The purpose of this research is to compare the effect of single-injection sciatic PNB to continuous sciatic PNB on 1) postoperative pain control as measured by self-reported pain scores, pain medication use, and unplanned hospital admission due to poor pain control, 2) active knee flexion, and 3) patient satisfaction with pain control following ACL reconstruction with a hamstring autograft. The findings of this study have the potential to guide informed clinical reasoning and decision making regarding sciatic peripheral nerve blockade techniques following hamstring autograft harvest in adolescents undergoing anterior cruciate ligament reconstruction.

I. BACKGROUND AND SIGNIFICANCE

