The intervention in this study will be one of two techniques for sciatic PNB: single-injection PNB or continuous sciatic PNB with a CPI catheter. The PNB protocol will be assigned by computer-generated randomization. All study participants will receive standard care, including standard anesthetic care as recommended by the American Society of Anesthesiologists and the American Association of Nurse Anesthetists, and the surgical procedures will be in accordance with those set forth by the American College of Surgeons. Anesthetic management will be left to the discretion of the clinical team providing anesthesia care, which includes, but is not limited to, the amount of inhalation anesthetic and intravenous opioids each study participant receives throughout the intraoperative portion of the study.

All sciatic PNB will be performed following the induction of general anesthesia, but prior to the end of anesthesia. For patients randomized to the single-injection sciatic PNB group, ultrasound will be utilized to identify the sciatic nerve in the sub-gluteal region. Once the sciatic nerve is identified, 1 mL/kg (to a maximum volume of 20 mLs) of 0.2% ropivacaine without epinephrine will be injected into the perineural space surrounding the sciatic nerve.

For patients randomized to the continuous sciatic PNB group, ultrasound will be utilized to assist the anesthesia team with placing the catheter tip adjacent to the sciatic nerve in the sub-gluteal region in preparation for continuous infusion of local anesthetic postoperatively. Once proper placement of the sciatic CPI catheter is verified, 1 mL/kg (to a maximum volume of 20 mLs) of 0.2% ropivacaine without epinephrine will be administered incrementally over two minutes. An infusion of 0.125% ropivacaine will be started at the end of surgery at a rate of 3-4 mL/hr (based on patient weight) for 48 hours postoperatively. While assessments will be made through 72 hours postoperatively, CPI catheters will only remain in-situ for 48 hours, as the incidence of infection increases should an indwelling CPI catheter remain greater than 48 hours (Jeng, Torrillo, & Rosenblatt, 2010).

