- Angioneurotic edema
- Tachycardia
- Sneezing
- Nausea
- Vomiting
- Elevated temperature
- Possibly anaphylactoid symptomology

Additionally, there is a low risk of mild discomfort or inconvenience to the subject, as they will receive regional blockade of some nature. Additionally, unforeseen risks may include, but are not limited to:

- Needle trauma
- Intraneural injection
- Intravascular injection
- Local anesthetic toxicity
- Hematoma
- Infection
- Poor/failed block

Finally, risks related to the use of a CPI catheter are rare, but include:

- Infection
- Infusion pump malfunction
- Local anesthetic toxicity
- Skin irritation or allergic reaction secondary to dressing material
- Unintentional CPI catheter dislodgement

- Fluid (local anesthetic) leakage at the CPI catheter insertion site
- Falls secondary to motor blockade

2. Risk Benefit Analysis:

Benefits: Subjects in this research study are unlikely to gain any personal benefit on the day of the study from their participation as the decisions of the clinical team caring for the patients will be guided by the randomized study protocol. The knowledge gained may be of benefit in the management of future adolescent patients who require ACL reconstruction. The ability to effectively provide pain control will lead to more efficient utilization of healthcare resources.

Study Related Risks: The risks associated with this study are minimal and are related to PNB. Both techniques of sciatic PNB included in this study are accepted techniques in clinical practice. All risks related to sciatic PNB are incidental, that is, associated with PNB, not the study itself as this is an observational study.

Risks/Benefit Analysis: It is the opinion of the principal investigator (PI) that this study is classified as “minimal risk but without direct benefit to participants”.

B. Subject Population:

A subject may be INCLUDED in this study if:

1. The subject is male or female;
2. The subject is of any racial or ethnic group;
3. The subject is age 10 years to 18 years (inclusive);
4. The subject is scheduled for the following:
Unilateral ACL reconstruction with a hamstring autograft under general anesthesia on an outpatient basis, and not being performed in conjunction with any other surgical procedures;
5. The subject is American Society of Anesthesiologists (ASA) patient classification I-II;

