date and time their leg was no longer numb behind their knee. The orthopedic surgeon performing the ACL reconstruction or a member of his orthopedic team will prescribe all postoperative oral pain medication. The oral pain medication typically prescribed is either Percocet or Vicodin. Vicodin, a schedule 3 controlled substance, is approximately half as potent as Percocet, which is a schedule 2 controlled substance. The patient will record the time and dose of all oral pain medication taken during the 72 hours postoperative period. The patient or their guardian will also record data regarding pain associated with active knee flexion once every 12 hours for 72 hours postoperatively. In addition, the patient or their guardian will record satisfaction with pain control once every 12 hours for 72 hours postoperatively.

The research coordinator may collect all data recorded by the patient and/or their guardian via telephone interview. Data will be collected using the same data collection tool given to the study participants to avoid instrumentation and maintain interrater reliability. Untoward events, such as unplanned hospital admission, CPI catheter dislodgement, or local anesthetic toxicity, will also be noted should they occur. This information will be collected from the patient or guardian once every 24 hours by the research coordinator during the 72-hour postoperative period; the postoperative period begins at the time of discharge from the PACU.

1. Survey(s) and Questionnaire(s):

Patients and their guardian will be given data collection instruments to complete postoperatively at the time of enrollment to facilitate recall when conveying information to the study staff during telephone conversations. The data collection instruments will be available in different languages and utilized for non-English speaking patients and/or guardians. The patient and their guardian(s) will receive training regarding the data collection tool both during the time of enrollment and again prior to discharge from the hospital. At the time of enrollment, essential phone numbers, including home phone and cell phone numbers, will be collected. Should the patient and/or guardian lose the data collection sheet, additional copies can be emailed to them upon request. Hospital-approved interpreters will be utilized for non-English speaking patients and/or guardian(s).

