investigational plan, or application (including a supplementary plan or application) or any other unanticipated serious problem associated with peripheral nerve blockade that related to the rights, safety or welfare of subjects. Refer to the Peripheral Nerve Blockade Risk Analysis and Risk Assessment section for details on anticipated adverse regional blockade effects.

B. Adverse Event Reporting:

All serious adverse events will be reported to the IRB per IRB reporting requirements. These reports may include, but will not be limited to: date of onset; brief description of the events; their treatment; whether they resulted in death, inpatient hospitalization, severe or permanent disability or were life threatening; their relationship to the study device; and resolution. All unanticipated adverse device effects will be reported to the IRB.

C. Data Safety Monitoring Plan:

In an effort to ensure patient safety throughout the course of this study, a Data Safety Monitoring Plan has been established. The Data Safety Monitoring Committee shall convene at predetermined intervals to assess the progress of the study for potential patient-related adverse events. Such events include, but are not limited to: infection at the CPI catheter insertion site, infusion pump malfunction, local anesthetic toxicity, skin irritation or allergic reaction secondary to CPI catheter dressings, and falls secondary to motor blockade. Should 2 or more study-related adverse events occur, the study will be suspended immediately pending review of the study and results to date by the Data Safety Monitoring Committee. In addition, should any unforeseen study-related adverse event not previously reported in the literature occur, the study will be stopped for review by the Data Safety Monitoring Committee. Should the study be stopped at any point, enrollment will not resume until the Data Safety Monitoring Committee has determined that it is safe to resume the study. In addition, at any point during the course of the study should the Data Safety Monitoring Committee determine that it is not in the best interest of adolescent patients undergoing ACL with a hamstring autograft to continue the study, the study will be stopped.

D. Data Safety Monitoring Committee:

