Appendix B

Post-Discharge Data Collection Instrument

PAIN CONTROL:

Keep track of your pain score and location of pain:

Pain score: 0 = no pain, 10 = worst pain			
Pain location: F = front of knee, B = back of knee, X = both front & back			
6 hours		42 hours	
12 hours		48 hours	
18 hours		54 hours	
24 hours		60 hours	
30 hours		66 hours	
36 hours		72 hours	

Date and time the leg was no longer numb behind the knee: _____

Pain medicine prescribed (circle one): Vicodin Percocet Other: _____

Write down every time pain medication is taken:

[illegible]

ACTIVE KNEE MOVEMENT:

Rate the ability to bend the knee that was operated on:

Knee Movement	12 hours	24 hours	36 hours	48 hours	60 hours	72 hours
0 = Able to bend with no pain						
1 = Able to bend, but with pain						
2 = Too much pain to bend						

SATISFACTION:

Rate your overall satisfaction score with pain management:

Satisfaction Score	12 hours	24 hours	36 hours	48 hours	60 hours	72 hours
0 = Not satisfied at all						
1 = Not satisfied						
2 = Partially satisfied						
3 = Satisfied						
4 = Highly satisfied						

From your perspective, have you encountered any unexpected postoperative experiences?

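### Falls and catheter-site infection are named for safety review but not prompted on the post-discharge form shown, and scheduled contact ends about 24 hours after the catheter period

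*Combined protocol and SAP*

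**What the plan says.** **Which harms matter.** The opening summary reports that advocates of single injection worry about effects of continuous block "such as decreased active knee flexion and increased risk of falls". Section V.A lists "Falls secondary to motor blockade" and infection among the catheter risks. It explains that "CPI catheters will only remain in-situ for 48 hours, as the incidence of infection increases" beyond that time. Section VII.C puts both harms on the committee's list, which includes "infection at the CPI catheter insertion site, infusion pump malfunction, local anesthetic toxicity" and falls from motor block. It also suspends the study at two or more study-related adverse events.

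**How they are collected.** Section V.G has the research coordinator gather untoward events every 24 hours. Its examples are an unplanned admission, a dislodged catheter and toxicity from the local anesthetic. The call uses the tool given to families. In Appendix B that tool covers pain score and location, when numbness behind the knee ended, pain medicine, knee bending and satisfaction. It ends with one open question: "From your perspective, have you encountered any unexpected postoperative experiences".

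**For how long.** Section V.G runs the calls over 72 hours, where "the postoperative period begins at the time of discharge from the PACU". Section VII adds: "Adverse events will be collected until data collection is complete". Study-related events already found are followed to completion.

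**How they are analyzed.** Section VI.B plans no between-arm summary of falls or site infection.

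**The concern.** A harm that is expected and already listed is poorly elicited by a question about the unexpected. Falls and site infection are both on the committee's list, yet neither is asked about by name on the form or given as an example for the call. The knee-bending item does not fill the gap, because all three of its responses grade pain and none records weakness or giving way.

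Patients know their assignment (Section V.A). Where harms are left to spontaneous mention, families may report differently by arm, in a direction that cannot be predicted. A standard question put to everyone reduces that risk.

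Contact also stops soon after the catheter period. A site infection, or a nerve deficit, that first appears later has no planned route into the data. At stake are the harm side of the comparison that motivates the trial and the counts on which the committee relies.

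**Working it through.** **1. Plan's own figure.** The plan computes nothing for harms. Its sample size reproduces: 2 × (1.960 + 0.842)² / 0.5² = 62.8, so 63 per group by the normal approximation and 64 by the t-test. The plan enrolls 70 per arm, 140 in all.

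**2. Committee list against collection tools.**

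| Harm | Committee list (VII.C) | Example for daily call (V.G) | Item in Appendix B |
|---|---|---|---|
| Falls | yes | no | no |
| Catheter-site infection | yes | no | no |
| Local anesthetic toxicity | yes | yes | no |

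**3. Observation after the catheter period.** Section V.A says "An infusion of 0.125% ropivacaine will be started at the end of surgery at a rate of 3-4 mL/hr" for 48 hours, while follow-up is timed from PACU discharge.
- Both clocks from PACU discharge: 72 − 48 = 24 h.
- Infusion clock from end of surgery, with an assumed PACU stay of 1 to 4 h: (72 + 1) − 48 = 25 h to (72 + 4) − 48 = 28 h.

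**4. Meaning of the end of data collection.** Section VII does not say whether it means each participant's data collection or the whole study's. Section X refers to completing it during the three days after surgery, which favors the per-participant reading. On either reading, no contact or record check after 72 h is described.

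**5. Catheters at risk.** Both arms have a femoral catheter and the continuous arm also has a sciatic one. As planned, that is 70 × 1 + 70 × 2 = 210 catheters, so site events need to be recorded by catheter as well as by arm.

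**6. Illustration of under-capture.** Let p be an assumed fall risk in all 140 patients, c the assumed share captured, and q = p × c. Then P(at least 2 seen) = 1 − (1 − q)^140 − 140q(1 − q)^139.

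| Assumed p | c = 100% | c = 75% | c = 50% |
|---|---|---|---|
| 1% | 41% | 28% | 16% |
| 2% | 77% | 62% | 41% |
| 5% | 99% | 97% | 87% |

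For p = 2% and full capture: 1 − 0.059 − 0.169 = 0.772. With half captured, q = 1%: 1 − 0.245 − 0.346 = 0.409.

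**7. What better capture could support.**
- No events in 70 patients gives a one-sided 95% upper bound of 1 − 0.05^(1/70) = 4.2%, valid only if capture is complete.
- For assumed risks of 2% and 5% at 70 per arm, the pooled standard error is √(2 × 0.035 × 0.965 / 70) = 0.0311 and the unpooled one is √((0.02 × 0.98 + 0.05 × 0.95) / 70) = 0.0310. Power is Φ[(0.03 − 1.96 × 0.0311) / 0.0310] = Φ(−1.00), about 16%.

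**The case against.** The case against is substantial, and much of it stands.

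- **Capture is not absent.** The examples for the daily call are an open list, research staff collect untoward events every day, and a fall fits the adverse event definition in Section VII.A. The adverse event case report form is not in the documents, so a fall field there cannot be excluded, although a field on a staff form does not by itself prompt a family. The instrument is also to be piloted and revised before enrollment.
- **Numbness is recorded.** The form asks when numbness behind the knee ended, so a reader who infers that a persistent deficit is never collected goes too far. What escapes is a deficit first appearing after 72 hours, or weakness without numbness. A blank entry is also ambiguous between continuing numbness and a missed answer.
- **Infection plays a different role from falls.** The opening summary weighs falls and reduced knee flexion against continuous block. Infection is the reason for the 48-hour limit and a listed risk. Knee flexion does have a hypothesis, a form item and a planned test, so the harm side is not empty.
- **No direction of bias is established.** Both arms have a femoral catheter, so under-counting can affect both. The documents do not show that it favors continuous block.
- **The illustration is limited.** Fall risk and capture share are assumptions. The chance of seeing two falls is also not the chance of reaching the suspension rule, which counts study-related adverse events of any kind.

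None of this supplies a prompted question or a check after 72 hours.

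**Conclusion.** The point holds as a gap in elicitation and follow-up. Two harms named for committee review are not prompted on the form shown, which also serves as the call tool, and scheduled contact ends about 24 hours after the catheter period (25 to 28 hours with an assumed PACU stay of 1 to 4 hours).

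The size of any under-count is unknown. The fall from 77% to 41% rests on an assumed 2% risk and 50% capture. At an assumed 5% risk, the chance of seeing two falls is still 87% with half captured. A reader might therefore infer that the trial would show few falls and almost no infections whatever the truth, but the documents do not support that.

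These harms are not endpoints and no hypothesis test depends on them. The change is a cheap improvement to safety monitoring and reporting, and it leaves the efficacy analysis untouched.

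**What to change.** 1. Add to Appendix B and to each daily call a yes/no item: *Did you fall or did your leg give way in the last 24 hours?*
2. Add a yes/no catheter-site item (redness, swelling, discharge), answered separately for each catheter.
3. State in Section VI that falls will be summarized descriptively by arm, and site events by arm and catheter site.
4. Where a later routine record exists, or data from the linked ACL outcomes study in Section XI for patients who consent to both, add one record check for late site infection and for persistent numbness or weakness. The documents describe no later visit and do not show what the linked study collects, so this step is secondary. Where no such source exists, say in the report that harms were observed only to 72 hours.
5. Clarify in Section VII whether the end of data collection refers to each participant or to the whole study.

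**Cost.** A few extra questions in calls already planned, and, for step 4, slightly longer record access with matching consent wording. No extra visit or procedure is needed. The result is descriptive: with 70 per arm it would not be a powered comparison.
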